3.8.2. Blinding/Unblinding

Pharmacokinetic data may be assessed during the study. Personnel responsible for bioanalysis will be provided with the randomization code in order to facilitate the analysis. However, the personnel responsible for bioanalysis will not have access to clinical safety and efficacy data and will provide concentration data to other personnel in a manner that will not identify individual patients (ie, a dummy patient identifier will be linked to an individual patient's concentration data).

For information about personnel who may be aware of treatment assignments, see Section 3.7. These individuals will not be involved in conduct of any study procedures or assessment of any adverse events.

In case of a serious adverse event or pregnancy, or in cases when knowledge of the study drug assignment is needed to make treatment decisions, the investigator may unblind the patient's drug assignment as deemed necessary, mainly in emergency situations. Individual treatment codes, indicating the treatment randomization for each randomized patient, will be available to the investigator(s) and/or pharmacist(s) at the study center via the IRT, both via telephone and internet. If possible, the sponsor should be notified of the event prior to breaking of the code. If this is not possible, the sponsor should be notified immediately afterwards, and the patient's drug code assignment should not be revealed. Breaking of the treatment code can always be performed by the site without prior approval by the sponsor.

When a blind is broken, the patient will be withdrawn from the study, and the event will be recorded onto the CRF. The circumstances leading to the breaking of the code should be fully documented in the investigator's study files and in the patient's source documentation. Treatment assignment should not be recorded in any study documents or source documents.

In blinded studies, for adverse events that are defined as suspected unexpected serious adverse reaction (SUSAR) (ie, reasonable possibility; see Section 7.1.4), Global Patient Safety & Pharmacovigilance may independently request that the treatment code be revealed (on a case-by-case basis) to comply with regulatory requirements. The report will be provided in an unblinded manner for regulatory submission. If this occurs, blinding will be maintained for the investigator and for other personnel involved in the conduct, analysis, and reporting of the data.

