3.9. Drugs Used in the Study

Additional details may also be found in the current version of the Investigator's Brochure for TEV-48125.

TEV-48125 will be provided as a sterile, unpreserved, colorless to slightly yellow, aqueous solution for injection, supplied in a 2.25-mL prefilled syringe for single-use administration, containing 150 mg/mL in 16±2.5 mM L-histidine, 0.2-mg/mL polysorbate 80, 84-mg/mL sucrose, and 0.136-mg/mL ethylenediaminetetraacetic acid (EDTA).

TEV-48125 will be administered sc at a dose of 225 mg at visits 2 through 13. Each dose will be separated by approximately 4 weeks (28 days). A more detailed description of administration procedures is given in Section 5.1.

This is an uncontrolled study with no other study drug.

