3.14.4. Procedures After Study Drug Treatment

3.14.4.1. Patients Rolling Over from the Pivotal Efficacy Studies and New Patients (Final Visit [Visit 15 (Day 533)])

Procedures after study drug treatment will be the same for patients rolling over from the pivotal efficacy studies who receive study drug during the current study and patients not rolling over from the pivotal efficacy studies.

Patients who participate in the study in compliance with the protocol for the entire treatment period (ie, from visit 2 through visit 14) will be considered to have completed the study. Patients may be treated with standard of care following completion of visit 14.

Patients who complete the treatment period will have a follow-up visit approximately 7.5 months (225 days [the approximate equivalent of 5 half-lives]) after administration of the final dose of study drug. The following procedures/assessments will be performed at this visit:

- Inquire about adverse events.
- Inquire about/review concomitant medications.
- Perform physical examination (including weight).
- Complete the eC-SSRS Since Last Visit version.
- Obtain a 4-mL blood sample for plasma TEV-48125 concentration determination.
- Obtain a 5-mL blood sample for serum ADA assessment.
- Obtain a 5-mL urine sample for biomarker analysis.
- Obtain an 18.5-mL blood sample (6 mL each for serum and plasma and 6.5 mL for RNA) for serum, plasma, and RNA biomarker analysis.

In addition, a single 6-mL blood sample for pharmacogenomics (DNA) may be obtained from patients who consent to pharmacogenomics analysis if the sample is not obtained at an earlier visit.

Patients who discontinue treatment prematurely must be encouraged to continue to attend the regular scheduled visits, and complete the prescribed safety and efficacy evaluations through the EOT visit and the follow-up visit, if at all possible.

Patients who both discontinue treatment and also withdraw from the study should have EOT (early withdrawal) visit procedures/assessments (see [Table 1](#) and [Table 2](#)) performed on the last day the patient receives the study drug, or as soon as possible thereafter. The patient should also return for the follow-up visit approximately 7.5 months after the last dose of study drug if at all possible.

Procedures for patients who withdraw prematurely from the study are described in [Section 4.4](#). As appropriate, patients should be treated with standard of care following termination of the study.

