When a blind is broken, the patient will be withdrawn from the study, and the event will be recorded onto the CRF. The circumstances leading to the breaking of the code should be fully documented in the investigator's study files and in the patient's source documentation. Treatment assignment should not be recorded in any study documents or source documents.

In blinded studies, for adverse events that are defined as suspected unexpected serious adverse reaction (SUSAR) (ie, reasonable possibility; see protocol Section 7.1.4), Global Patient Safety & Pharmacovigilance may independently request that the treatment code be revealed (on a case-

by-case basis) to comply with regulatory requirements. The report will be provided in an unblinded manner for regulatory submission. If this occurs, blinding will be maintained for the investigator and for other personnel involved in the conduct, analysis, and reporting of the data.

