4.6. Study Days and Visit Windows

Study days will be numbered relative to the 1st day of study drug administration. The start of treatment (visit 2 or day 1) is defined as the date on which a patient receives the 1st dose of study drug, as recorded on the study drug diary. The 1st day for the patients rolling over from the pivotal efficacy studies will be the day when they receive the 1st dose of study drug after finishing their procedures/assessments for the pivotal study EOT visit ([Figure 1](#) and [Figure 2](#)). Days will be numbered relative to study start (ie, ..., -2, -1, 1, 2, ...; with day 1 being the start of study drug and day -1 being the day before the start of study drug).

The 4-week (28-day) visit windows for the e-diary based efficacy endpoints will be determined based on the actual dosing day. The run-in phase for the new patients is defined as day -28 to -1 before the 1st injection on day 1. Treatment is from the visit 2 to visit 14 or the EOT visit. Month 1 is from the date/time of the 1st dose of study drug administration on day 1 to the date/time just

before the 2nd dose. Month 2 is from the date/time of the 2nd dose to the date/time just before the 3rd dose. Month 3 is from the date/time of the 3rd dose, and so on.

Throughout this document, all by month efficacy summaries for the headache data will refer to these visit windows.

For all other by-visit summaries, if there are multiple assessments at a postbaseline visit then the last non-missing assessment at that visit will be used for the summary. This includes assessments at the scheduled and unscheduled visits.

Endpoint for analyses and summaries is the last observed postbaseline data. For patients who withdraw from the study, their safety data at the early termination visit will be excluded from the by-visit summaries but will be included in the endpoint summaries.

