7.2. Study Drug Administration

Patients rolling over from the pivotal efficacy studies who were randomized to the active treatment groups will continue receiving the same treatment (ie, monthly TEV-48125 at 225 mg or quarterly TEV-48125 at 675 mg) throughout this long-term safety and efficacy study. Patients rolling over from the pivotal efficacy studies who received placebo and the new patients will be randomly assigned in a 1:1 ratio using IRT as follows:

- Patients with CM will receive sc TEV-48125 at 675 mg (loading dose) followed by 11 monthly sc doses of TEV-48125 at 225 mg or sc TEV-48125 at 675 mg once every 3 months for 12 months for a total of 4 doses.
- Patients with EM will receive monthly sc TEV-48125 at 225 mg for 12 months or sc TEV-48125 at 675 mg once every 3 months for 12 months for a total of 4 doses

Study drug will be administered as sc injections approximately every 4 weeks (28 days).

In order to maintain the study blind, all patients will receive 3 injections at visits 2, 5, 8, and 11 and 1 injection at all other visits as detailed in [Table 5](#).

Table 5: Study Drug Administration by Treatment Group and Visit

Treatment group in this study	Visit 2	Visits 5, 8, and 11	Visits 3, 4, 6, 7, 9, 10, 12, and 13
Loading dose of TEV-48125 at 675 mg followed by monthly TEV-48125 at 225 mg	3 active injections (225 mg/1.5 mL)	1 active injection (225 mg/1.5 mL) and two 1.5-mL placebo injections	1 active injection (225 mg/1.5 mL)
Monthly TEV-48125 at 225 mg	1 active injection (225 mg/1.5 mL) and two 1.5-mL placebo injections	1 active injection (225 mg/1.5 mL) and two 1.5-mL placebo injections	1 active injection (225 mg/1.5 mL)
Quarterly TEV-48125 at 675 mg	3 active injections (225 mg/1.5 mL)	3 active injections (225 mg/1.5 mL)	one 1.5-mL placebo injection

Duration of treatment (days treated) is the number of days on treatment based on the first and EOT visit day/early withdrawal day (EOT visit day – first day of study drug + 1). For subjects who are lost to follow-up, the last day is defined as the last study drug administration date +27.

Number (%) of patients receiving ≥ 1 dose, ≥ 2 doses, ≥ 3 doses, and so on will be summarized using descriptive statistics by treatment group. Duration of treatment (days) and number of doses will also be summarized using descriptive statistics for each treatment group.

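### An investigator code break removes the patient from the study, not only from study drug, and so ends interim safety visits that other treatment discontinuers are encouraged to keep (low priority)

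*Protocol*

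**What the plan says.** Protocol 3.8.2 lets the investigator break the code after a serious adverse event, for a pregnancy, or when a treatment decision requires it. The consequence is then fixed: "When a blind is broken, the patient will be withdrawn from the study, and the event will be recorded onto the CRF". SAP 2.4.2 repeats it: "When a blind is broken, the patient will be withdrawn from the study". When pharmacovigilance asks for the code of a suspected unexpected serious reaction, the investigator stays blinded and no withdrawal is stated, so the rule bears on investigator code breaks.

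Protocol 3.14.4.1 separates two groups. For those who stop drug only: "Patients who discontinue treatment prematurely must be encouraged to continue to attend the regular scheduled visits", with safety and efficacy evaluations continuing through EOT and follow-up where possible. For the others: "Patients who both discontinue treatment and also withdraw from the study should have EOT (early withdrawal) visit procedures/assessments", followed by a request to return about 7.5 months after the last dose. A code-broken patient falls into the second group.

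On what the code can reveal, Protocol 3.9 states: "This is an uncontrolled study with no other study drug".

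On exposure, SAP 7.2 states: "Duration of treatment (days treated) is the number of days on treatment based on the first and EOT visit day/early withdrawal day". It adds one exception: "For subjects who are lost to follow-up, the last day is defined as the last study drug administration date +27".

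**The concern.** The primary objective is long-term safety. Patients whose code is broken are selected partly by serious adverse events, so their later laboratory values, vital signs and suicidality assessments are of interest to a safety study. The plan keeps scheduled collection open for patients who stop drug for other reasons and closes it for these, without giving a reason. Every treated patient receives TEV-48125 and no inferential analysis is planned (Protocol 9.6), so an investigator's knowledge of one patient's regimen is not an evident reason to stop measuring that patient.

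Keeping these patients in the study also draws attention to SAP 7.2. Its duration formula has no provision for someone who stops drug but stays to visit 14, a group that 3.14.4.1 already creates.

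**Working it through.** **Inputs**
- Visit k falls on day 28(k − 2): visit 2 is day 0, visit 5 day 84, visit 13 day 308 and visit 14 day 336 (Protocol Tables 1 and 2).
- Vital signs and eC-SSRS are scheduled at every visit from 3 to 14. Laboratory tests are at visits 4, 6, 8, 10, 12 and 14 (same tables).
- The early withdrawal visit uses the visit 14 assessments, on the last dosing day or as soon as possible afterwards (3.14.4.1).
- The 7.5-month visit has adverse events, physical examination, eC-SSRS and PK, ADA and biomarker samples. It has no clinical laboratory tests, vital signs or ECG.

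**Step 1: scheduled data lost after a last dose at visit k.** Visits k + 1 to 14 number 14 − k. One set is recovered at the early withdrawal visit, so the net loss is (14 − k) − 1 = 13 − k visits. The laboratory loss is the number of laboratory visits after k, minus 1.

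| Last dose at visit k | Visits lost, 13 − k | Laboratory sets lost |
|---|---|---|
| 2 | 11 | 6 − 1 = 5 |
| 5 | 8 | 5 − 1 = 4 |
| 8 | 5 | 3 − 1 = 2 |
| 11 | 2 | 2 − 1 = 1 |
| 13 | 0 | 1 − 1 = 0 |

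For k = 5 that is 8 vital-sign sets, 8 eC-SSRS assessments and 4 laboratory sets. These are ceilings, because continued attendance is only encouraged.

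**Step 2: what remains.** Adverse events are recorded through the 7.5-month visit (7.1.2). Events leading to withdrawal are monitored at the investigator's discretion (4.4, 7.1.7). The early withdrawal assessments are done, the 7.5-month visit is requested (3.1, 3.14.4.1, 4.4) and unscheduled visits are allowed (3.14.5).

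**Step 3: whom the rule affects.** Only patients who would otherwise have stayed. Pregnant patients are withdrawn under 7.3.5.1 in any case. Patients meeting a liver stopping rule go to early withdrawal activities under Appendix E.

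**Step 4: treatment duration under SAP 7.2 (a separate matter).** The formula is EOT visit day − first dosing day + 1. For a patient who stops drug but attends visit 14 it gives 336 − 0 + 1 = 337 days, whatever k is. The SAP's lost-to-follow-up rule gives 28(k − 2) + 27 − 0 + 1 = 28(k − 1).

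| k | SAP 7.2 at visit 14 | Last administration + 27 | Difference |
|---|---|---|---|
| 2 | 337 | 28 | 309 |
| 5 | 337 | 112 | 225 |
| 13 | 337 | 336 | 1 |

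For the quarterly regimen the active doses are at visits 2, 5, 8 and 11, which are 84 days apart, so the matching extension is +83 days from the last active dose. With that dose at visit 5: 84 + 83 − 0 + 1 = 168 days, and the excess is 337 − 168 = 169. A full course agrees under both extensions: monthly 308 + 27 + 1 = 336; quarterly 252 + 83 + 1 = 336.

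Under the present code-break rule, a patient whose early withdrawal visit is on the day of a visit 5 dose counts 84 − 0 + 1 = 85 days. The code-break rule therefore does not cause the overcount.

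**The case against.** The case for leaving the rule alone is substantial. The study is descriptive, code breaks are meant mainly for emergencies, and the data lost are routine interim measurements that other discontinuers are only encouraged to provide. An investigator may also withdraw a patient for an adverse event without any code break (3.12, 7.1.7). All of this stands, and it is why the point is low priority.

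A reader might infer that safety follow-up stops at the code break. It does not; step 2 lists what continues.

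A reader might also infer that the code reveals nothing beyond the current regimen. That fails for CM rollovers on a monthly regimen. Those who had active monthly drug in the pivotal study continue at 225 mg without a new load, while former placebo patients assigned to monthly dosing receive 675 mg at visit 2 (Protocol 3.1 and Table 4). For them the code also discloses the pivotal-study assignment. This is a real blinding interest, but withdrawal does not undo the disclosure, and the documents do not offer it as a reason to stop safety collection.

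On exposure, it is fair to object that the overcount is not produced by the code-break rule, and that a flat +27 days would cut off a quarterly patient one month into a three-month dose. Both objections are accepted. It can also be said that the date of withdrawal from drug is recorded separately (4.4) and that number of doses is tabulated beside duration. Those data make a correction possible, but the SAP formula does not use them.

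Finally, a reader might take the SAP 4.6 sentence "Treatment is from the visit 2 to visit 14 or the EOT visit" to mean that all data through EOT are classed as on-treatment, and ask for an off-treatment flag on that basis. The sentence sits in the paragraph that defines windows for the e-diary efficacy endpoints; other by-visit summaries are handled in a later paragraph. It does not support that reading.

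**Conclusion.** The point holds as a cheap improvement of low priority. After an investigator code break, a patient who would otherwise have stayed loses at most 13 − k scheduled visits (0 to 11) and 0 to 5 laboratory sets. These figures assume full attendance and an early withdrawal visit that recovers one set. The number of code breaks is not given and is probably small. It would go too far to say that the rule biases the safety results: no bias can be derived, and no conclusion is shown to change.

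The SAP 7.2 overcount is a separate matter and applies to any patient who stops drug and stays to visit 14 under 3.14.4.1. For a last dose at visit 5 it is 225 days by the SAP's own +27 rule, or 169 days for a quarterly patient credited with the full dosing interval. It rests on applying the formula as written, with the EOT visit day as the end date.

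**What to change.** 1. In Protocol 3.8.2 and SAP 2.4.2, replace withdrawal from the study with: *discontinued from study drug and encouraged to continue scheduled visits under Section 3.14.4.1 unless consent is withdrawn*. Leave the pregnancy and liver stopping rules unchanged.
2. In SAP 7.2, for patients who stop drug early but stay in the study, end treatment duration at the last administration plus the dosing interval: +27 days for monthly dosing, and about +83 days after the last active 675-mg dose for quarterly dosing. This is worth doing even if item 1 is not adopted. If item 1 is adopted, item 2 should go with it, because code-broken patients who stay would otherwise be overcounted too.

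The cost is one sentence in the next protocol amendment, the same sentence in SAP 2.4.2, one sentence in SAP 7.2 and minor programming. The downside is that a few patients keep visits already on the schedule. One side effect is that SAP 6.4.1.1 counts patients who leave the study early as non-responders, so a code-broken patient who stays would no longer fall under that rule automatically. This touches exploratory endpoints only.

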3.8.3. Data Monitoring Committee

This is not applicable.

3.9. Drugs Used in the Study

Additional details may also be found in the current version of the Investigator's Brochure for TEV-48125.

TEV-48125 will be provided as a sterile, unpreserved, colorless to slightly yellow, aqueous solution for injection, supplied in a 2.25-mL prefilled syringe for single-use administration, containing 150 mg/mL in 16±2.5 mM L-histidine, 0.2-mg/mL polysorbate 80, 84-mg/mL sucrose, and 0.136-mg/mL ethylenediaminetetraacetic acid (EDTA).

TEV-48125 will be administered sc at a dose of 225 mg at visits 2 through 13. Each dose will be separated by approximately 4 weeks (28 days). A more detailed description of administration procedures is given in Section 5.1.

This is an uncontrolled study with no other study drug.

3.10. Drug Supply and Accountability

3.10.1. Drug Storage and Security

The study drug (TEV-48125) must be stored refrigerated at 2°C to 8°C (36°F to 46°F), protected from light; the site should have a process for monitoring the drug storage temperature.

TEV-48125 supplies must be kept in a secure area (eg, locked refrigerator).

3.10.2. Drug Accountability

Each study drug shipment will include a packing slip listing the contents of the shipment, drug return instructions, and any applicable forms.

Each investigator is responsible for ensuring that deliveries of study drug and other study materials from Teva are correctly received, recorded, handled, stored, accounted for, and used in accordance with this protocol. In addition, each investigator is responsible for ensuring that study drug and other material from Teva are correctly disposed of, safely and properly in accordance with local regulation.

A record of study drug accountability (ie, study drug and other materials received, used, retained, returned, or destroyed) must be prepared and signed by the principal investigator or designee, with an account given for any discrepancies.

3.11. Duration of Patient Participation and Justification

This study will consist of a 28-day run-in period (only for patients not rolling over from the pivotal efficacy studies) and a 12-month treatment period. Patients will be followed for 7.5 months (225 days) after administration of the final dose of study drug (ie, a 6.5-month follow-up period) for collection of pharmacokinetic, immunogenicity, and biomarker samples and inquiries about adverse events and concomitant medication use. It is considered that, with a half-life of around 45 days, there will be a complete washout of the drug from the circulating blood in 7.5 months (≥ 5 half-lives), allowing a more precise evaluation of ADA.

Patients are expected to participate in this study for its entire duration, which is a minimum of 18.5 months for patients rolling over from the pivotal efficacy studies or 19.5 months for patients not rolling over from the pivotal efficacy studies. In addition, patients rolling over from the pivotal efficacy studies for ADA evaluation only will participate in the current study for approximately 7.5 months. See Section 12.4 for the definition of the end of the study.

3.12. Stopping Rules and Discontinuation Criteria

There are no formal rules for early termination of this study. During the conduct of the study, serious adverse events will be reviewed (see Section 7.1.5) as they are reported from the investigational center to identify safety concerns. The study may be terminated by the sponsor at any time.

A patient may discontinue participation in the study at any time for any reason (eg, lack of efficacy, consent withdrawn, and adverse event). The investigator and/or sponsor can withdraw a patient from the study at any time for any reason (eg, protocol violation or deviation as defined in Section 11.1.2, noncompliance, or adverse event). In addition, patients with abnormal hepatic laboratory values (eg, ALT, AST, ALP, gamma-glutamyl transpeptidase [GGT], total bilirubin,

or international normalized ratio [INR]) may meet criteria for discontinuation from the study drug as summarized in [Appendix E](#).

